•	To evaluate DCR of MORAb-202 in participants with previously treated, metastatic NSCLC AC	•	DCR by RECIST 1.1 per investigator assessment

Main Estimand for the Secondary Objective^a

- Treatment: MORAb-202, 25 mg/m²
- Population: Participants with previously treated, metastatic NSCLC AC with evaluable baseline tumor assessment
- Variable: BOR, defined as the best response, as determined by investigator, recorded between the date of first dose and the date of first objectively documented progression per RECIST 1.1
- Intercurrent events: Early discontinuation of study treatment
 - Strategy to handle intercurrent events: treatment policy (all post-baseline tumor assessment regardless of on-treatment status will contribute to BOR determination)
- Intercurrent events: Initiation of subsequent anticancer therapy (excluding allowed palliative radiotherapy/surgery to non-target/non-thoracic sites)
 - Strategy to handle intercurrent events: treatment policy (all post-baseline tumor assessment regardless of initiation of subsequent anticancer therapy will contribute to BOR determination)
- Population-level summary: DCR, defined as the number of participants who achieve a BOR of confirmed CR, confirmed PR, or stable disease (SD), based on investigator assessments (using RECIST 1.1) divided by the number of all response evaluable participants, with two-sided 95% exact CI
- To evaluate duration of response (DoR) of MORAb-202 in participants with previously treated, metastatic NSCLC AC who achieved a CR or PR
- DoR by RECIST 1.1 per investigator assessment

Main Estimand for the Secondary Objective^a

- Treatment: MORAb-202, 25 mg/m²
- Population: Participants with previously treated, metastatic NSCLC AC with a best overall response as PR or CR
- Variable: DoR, defined as the time between the date of first documented response (CR or PR) that is subsequently confirmed, to the date of the first objectively documented tumor progression as determined by investigator (per RECIST 1.1), or death due to any cause, whichever occurs first. DoR will be evaluated for responders (confirmed CR or PR) only
- Intercurrent events: Early discontinuation of study treatment
 - Strategy to handle intercurrent events: Treatment policy (consider time of first PD or death as DoR event regardless of treatment discontinuation)
- Intercurrent events: Initiation of subsequent anticancer therapy (excluding allowed palliative radiotherapy/surgery to non-target/non-thoracic sites)
 - Strategy to handle intercurrent events: Treatment policy (consider time of first PD or death as DoR event regardless of initiation of subsequent anticancer therapy)

Protocol Amendment No.: 03

Table 4-1: Objectives, Endpoints and Estimands

Table 4-1: Objectives, Endpoints and Estimands		
	Objectives	Endpoints
	Population-level summary: KM estimated median response time and landmark	nark response rate of DoR

Protocol Amendment No.: 03

Table 4-1: Objectives, Endpoints and Estimands

Objectives	Endpoints

^a Sensitivity estimators of the main estimand and supplemental estimands will be defined in the Statistical Analysis Plan, where applicable.

Protocol Amendment No.: 03

5 STUDY DESIGN

[figure not shown]
5.1 Overall Design

CA116003 is a Phase 2 open-label, multicenter study assessing the safety, efficacy, and tolerability of MORAb-202 in participants with previously treated, metastatic NSCLC AC. Participants will receive MORAb-202 at a dose of 25 mg/m² every 3 weeks. The

- Eligible participants must have received prior treatment, including platinum-based chemotherapy and:
 - If without actionable genetic alterations or unknown genetic alterations status, treatment with anti-PD-1/PD-L1
 OR
 - If with known actionable genetic alterations, treatment with at least 1 targeted therapy
- Participants must have received no more than 3 prior lines of systemic therapy in the metastatic setting

NOTE: Participants with resectable or stage 3 locally advanced disease that has recurred or progressed within 1 year from the start of treatment with platinum-based chemotherapy and anti-PD-1/PD-L1 are not required to be retreated in the metastatic setting to be eligible.

The full eligibility criteria are described in Section 6.

FR α expression levels will be analyzed by immunohistochemistry (IHC) on an ongoing basis. There is no minimum requirement for FR α expression (%). A tumor sample of sufficient quality and quantity is highly recommended. An archival sample resubmission beyond the screening period for participants without tumor sample of sufficient quality and quantity who

Protocol Amendment No.: 03

Date: 07-Apr-2023 58

are otherwise eligible for the study is highly recommended Additional details on tumor sample quality and quantity metrics and logistics will be provided in the laboratory manual.

All participants will be treated until disease progression per RECIST 1.1 criteria as assessed by the investigator, unacceptable toxicity, participant withdrawal of consent for receiving study treatment, death, or the end of study, whichever occurs first. Maximum treatment duration will be up to 2 years; however, continuous safety and tumor assessment evaluation will guide the Sponsor's decision for a participant to be treated with additional cycles of study therapy beyond 2 years, if the participant has confirmed clinical benefit (see Section 7.8).

[figure not shown]
Al

relevant data (safety, efficacy, PK, and pharmacodynamics) will inform the Sponsor's decision on subsequent clinical development, including enrollment of additional participants into an expansion cohort to assess the relationship with FR α expression through a protocol amendment or continuing development in a separate study (see Section 10.1).

The primary analysis will be performed when all participants have been followed up for a minimum of 6 months or discontinued earlier from treatment. One dose level of MORAb-202 will be selected at the primary analysis to continue further evaluation. The dose selection will be based on the totality of efficacy and safety data and as described in Section 10.1. Safety follow-up visits will be conducted 30 days after the last study drug administration. All ongoing treatment-related SAEs and ILD/pneumonitis events will be followed until resolution or stabilization. All participants discontinuing treatment for reasons other than disease progression will be followed for continued tumor imaging assessments until investigator-assessed disease progression per RECIST 1.1, death, or withdrawal of consent for tumor assessment, whichever occurs first. All participants will be followed for survival every 3 months until the last participant has completed 2 years of survival follow-up.

The study design schematic is presented in Figure 5.1-1.

Figure 5.1-1: Study Design Schema

Physical examinations, vital sign measurements, and clinical laboratory evaluations will be performed at selected times throughout the treatment period. Participants will be closely monitored for AEs throughout the study. Blood samples will be collected for PK analysis. See Section 2 for more detail.

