Doses of MORAb-202 may be reduced, interrupted, delayed, or discontinued depending on how well the participant tolerates the treatment, as specified in the protocol.

Safety follow-up visits will be conducted 30 days after the last study drug administration. All ongoing treatment-related serious AEs and ILD events will be followed until resolution or stabilization. Survival follow-up visits will occur every 3 months (± 14 days) from safety follow-up, for up to 2 years, or until death, loss to follow-up, withdrawal of consent, or conclusion of the study, whichever occurs first. All participants discontinuing treatment for reasons other than disease progression will be followed for continued tumor assessments until investigator-assessed disease progression per Response Evaluation Criteria in Solid Tumors 1.1, death, or withdrawal of consent for tumor assessment, whichever occurs first.

End of study is defined as all treated participants who complete their last visit or scheduled procedure. Study completion is defined as the final date on which data for the endpoint of overall

Protocol Amendment No.: 03

survival were or are expected to be collected if this is not the same. A participant is considered to have completed the study if he/she has completed all survival follow-up visits.

Study Intervention:

Name					
Intervention Name/ Unit Dose Strength(s)	MORAb-202 (BMS-986445)/ [mg/ml]				
Туре	Drug				
Dose Formulation	Lyophilized powder in a single use vial				
Dosage Level(s)	$25 \text{ mg/m}^2 \text{ Q3W}$				
Route of Administration	IV infusion				
Use	Experimental				
IMP and NIMP/AxMP	IMP				
Sourcing	Provided centrally by the Sponsor				

Abbreviations: AxMP, auxiliary medicinal product; IMP, investigational medicinal product; IV, intravenous; NIMP, non-investigational medicinal product; Q3W, every 3 weeks.

Statistical Methods:

The primary endpoints are being assessed based on a targeted

The primary analysis will be performed when all participants in each arm have been followed up for a minimum of 6 months or discontinued earlier from treatment.

Data Monitoring Committee: No

A Data Monitoring Committee will not be used in the study.

Other Committee: Yes

A SC, and SSC will be used in this study.

Brief Summary:

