Procedure ^a	Day 1 - 3 days	Day 8 ± 3 days	Day 15 ± 3 days	Day 1 ± 3 days	(EOT) ^b	Notes ^c
Pregnancy Test (Women of Childbearing Potential [WOCBP] only)	X	See 1	See Notes			Serum or urine pregnancy test (minimum sensitivity equivalent units 25 IU/L or equivalent units of human chorionic gonadotropin [HCG]) to be performed within 24 hours prior to first dose of study treatment and then every 4 weeks (± 1 week) regardless of dosing schedule. If a urine test cannot be confirmed as negative (eg, an ambiguous result), a serum pregnancy test is required. Refer to Appendix 4 for further information.

Date: 07-Apr-2023

Approved v4.0 930184408 4.0

Table 2-2: On Treatment Procedural Outline (CA116003)

D 1 8		Cycle 1		Cycle 2 end of treatment		N C		
Procedure ^a	Day 1 - 3 days	Day 8 ± 3 days	Day 15 ± 3 days	Day 1 ± 3 days	(EOT) ^b	Notes ^c		
Efficacy Assessments								
						Contrast enhanced CT of the other known and/or suspected sites of disease should occur every 6 weeks (\pm 7 days) starting from first dose for the first 36 weeks, then every 12 weeks (\pm 7 days) until investigatorassessed disease progression and treatment discontinuation, whichever occurs later.		
Body Imaging See Notes					This schedule should be followed even if treatment delay occurs. In the event of unscheduled imaging, efforts should be made to return to the planned schedule for subsequent visits.			
						See Section 9.1.1 for further details and exceptions.		
Brain Imaging			See Notes			Participants with a history of brain metastasis or symptoms should have a surveillance magnetic resonance imaging (MRI; without and with contrast) per standard of care (approximately every 12 weeks), or sooner if clinically indicated. CT of the brain without and with contrast can be performed if MRI is contraindicated. See Section 9.1.1 for further details.		
					I			

930184408 4.0

Protocol Amendment No.: 03

Date: 07-Apr-2023

Approved v4.0 9301

Table 2-2: On Treatment Procedural Outline (CA116003)

		Cycle 1		Cycle 2 onwards	End of	
Procedure ^a	Day 1 - 3 days	Day 8 ± 3 days	Day 15 ± 3 days	Day 1 ± 3 days	(EOI)	Notes ^c
Study Intervention						
Contact Interactive Response Technology (IRT) for Treatment and Vial Assignment/Dispense/	X			X		Participants must receive the first dose of study treatment (MORAb-202) within 3 calendar days from treatment assignment in IRT, unless previously discussed with Medical Monitor (or designee).

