4 OBJECTIVES AND ENDPOINTS

Table 4-1: Objectives, Endpoints and Estimands

Objectives	Endpoints	
Primary	Primary	
To assess safety and tolerability of MORAb-202 in participants with previously treated, metastatic non-small cell lung cancer (NSCLC) adenocarcinoma (AC)	Incidence of treatment-related adverse events (TRAEs) leading to study treatment discontinuation	

Main Estimand for the Primary Objective^a

- Treatment: MORAb-202, 25 mg/m²
- Population: Participants with previously treated, metastatic NSCLC AC
- Variable: Occurrence of TRAEs leading to study treatment discontinuation
- Intercurrent events: Early discontinuation of study treatment due to reasons other than TRAE leading to treatment discontinuation
 - Strategy to handle intercurrent events: While on treatment (early discontinuation of treatment due to reasons other than TRAEs would not be counted towards population-level summary)
- Population-level summary: Adverse event (AE) incidence rate;
- To assess tumor response of MORAb-202 in participants with previously treated, metastatic NSCLC AC
- Objective response rate (ORR) by Response Evaluation Criteria in Solid Tumors (RECIST) 1.1 per investigator assessment

Main Estimand for the Primary Objective^a

- Treatment: MORAb-202, 25 mg/m²
- Population: Participants with previously treated, metastatic NSCLC AC with evaluable baseline tumor assessment
- Variable: Best overall response (BOR), defined as the best response, as determined by investigator, recorded between the date of first dose and the date of first objectively documented progression per RECIST 1.1
- Intercurrent events: Early discontinuation of study treatment
 - Strategy to handle intercurrent events: Treatment policy (all post-baseline tumor assessment regardless of on-treatment status will contribute to BOR determination)
- Intercurrent events: Initiation of subsequent anticancer therapy (excluding allowed palliative radiotherapy/surgery to non-target/non-thoracic sites)
 - Strategy to handle intercurrent events: Treatment policy (all post-baseline tumor assessment regardless of initiation of subsequent anticancer therapy will contribute to BOR determination)

Protocol Amendment No.: 03

Table 4-1: Objectives, Endpoints and Estimands

	Objectives	Endpoints	

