9.1.2 Imaging Assessments

[figure not shown]
Screening and on study images should be acquired as outlined in Section 2 Schedule of Activities.

On-treatment images should be assessed by the local team for

Collect any additional imaging that may demonstrate tumor response or progression (including scans performed at unscheduled timepoints and/or at an outside institution) for RECIST 1.1 tumor assessment and submit to the imaging vendor. Tumor assessments should continue on the protocoldefined imaging schedule, regardless of whether dosing is delayed or discontinued, until investigator-assessed disease progression by RECIST 1.1. Changes in tumor measurements and tumor responses will be assessed by the same investigator or designee using RECIST 1.1 criteria. Investigators will report the number and size of new lesions that appear while on study. The timepoint of tumor assessments will be reported on the eCRF based on the investigator's assessment using RECIST 1.1 criteria (see Appendix 6 for specifics of RECIST 1.1 criteria to be used in this study). Assessments of PR and CR must be confirmed at least 4 weeks (28 days) after initial response. A BOR of SD requires a minimum of 35 days on study from first dose to the date of the first imaging assessment.

Refer to Section 9.4.5 for details of

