10.2 Analysis Sets

For the purposes of analysis, the following populations are defined:

Analysis Sets	Description
Enrolled	All participants have agreed to participate in the clinical study following completion of the informed consent process, unless otherwise specified by the protocol.
All Treated	All participants who received at least 1 dose of study intervention. This will be the primary analysis set for safety objectives.
All Response Evaluable	All treated participants with baseline tumor assessment. This will be the primary analysis set for efficacy objectives.

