2.3.3 Best Overall Response

Best response determination of complete or partial response requires confirmation: Complete or partial responses may be claimed only if the criteria for each are met at a subsequent time point of ≥ 4 weeks (28 days) later. In this circumstance, the best overall response can be interpreted as in Table 2.3.3-1. When SD is believed to be best response, it must meet the protocol specified minimum time from the date of first treatment or

For example, if the first scheduled follow-up imaging visit is Week 6 (\pm 7 days) for a particular protocol, a Best Response of SD can only be made after the subject is on-study for a minimum of 6 weeks (42 days) minus 7 days, for an absolute minimum time on-study of 35 days from the reference start date (reference date is considered Day 1 on study). If the subject is not on-study for at least this amount of time, any tumor assessment indicating stable disease before this time period will have a Best Response of NE unless PD is identified.

Special note on response assessment: When nodal disease is included in the sum of target lesions and the nodes decrease to 'normal' size (< 10 mm), they may still have a measurement reported on scans. This measurement should be recorded even though the nodes are normal in order not to overstate progression should it be based on increase in size of the nodes. As noted earlier, this means that patients with CR may not have a total sum of 'zero' on the case report form (CRF).

Table 2.3.3-1:	Best Overall Response (Confirmation of CR and PR Required)			
Overall Response First Time Point	Overall Response Subsequent Time Point	Best Overall Response		
CR	CR	CR		
CR	PR	SD, PD OR PR ^a		
CR	SD	SD provided minimum criteria for SD duration met, otherwise, PD		
CR	PD	SD provided minimum criteria for SD duration met, otherwise, PD		
CR	NE	SD provided minimum criteria for SD duration met, otherwise, NE		
PR	CR	PR		

Protocol Amendment No.: 03

Table 2.3.3-1:	Best Overall Response (Confirmation of CR and PR Required)			
Overall Response First Time Point	Overall Response Subsequent Time Point	Best Overall Response		
PR	PR	PR		
PR	SD	SD		
PR	PD	SD provided minimum criteria for SD duration met, otherwise, PD		
PR	NE	SD provided minimum criteria for SD duration met, otherwise, NE		
NE	NE	NE		
CR = complete response, PR = partial response, SD = stable disease, PD = progressive disease, and NE = not evaluable.				

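### The primary-analysis trigger counts anyone off treatment as complete, yet ORR still uses their later scans, so the data cut can precede a late response confirmation

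*Combined protocol and SAP*

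**What the plan says.** Section 5.1 (Overall Design) schedules the primary analysis for when all participants have been "followed up for a minimum of 6 months or discontinued earlier from treatment". The Protocol Summary (Statistical Methods) repeats the rule, still worded by arm: "The primary analysis will be performed when all participants in each arm have been followed up for a minimum of 6 months", with the same alternative for those who stopped treatment. Neither place limits the reason for stopping. Section 5.1 also has one dose level selected at this analysis.

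Other parts of the plan keep collecting response data after treatment ends:

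- **Imaging.** Under Section 5.1, participants who stop for a reason other than progression "will be followed for continued tumor imaging assessments until investigator-assessed disease progression per RECIST 1.1", death or withdrawal of consent for tumor assessment.
- **Estimand.** For early treatment discontinuation, the ORR estimand in Table 4-1 uses a treatment-policy strategy: "all post-baseline tumor assessment regardless of on-treatment status will contribute to BOR determination".
- **Schedule.** In Table 2-2, body scans are every 6 weeks (±7 days) "starting from first dose for the first 36 weeks, then every 12 weeks". The schedule holds even if dosing is delayed.
- **Confirmation.** Section 9.1.2: "Assessments of PR and CR must be confirmed at least 4 weeks (28 days) after initial response".
- **Denominator.** The response-evaluable set in Section 10.2 is "All treated participants with baseline tumor assessment", so a missing later scan does not remove anyone.
- **Unconfirmed response.** Appendix 6, Table 2.3.3-1, scores a PR followed by a non-evaluable time point as "SD provided minimum criteria for SD duration met, otherwise, NE".

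**The concern.** The trigger and the primary efficacy estimand use different definitions of complete. A participant who stops for toxicity without progression satisfies the trigger on the day treatment stops. The estimand still expects scans from that participant, and one of them may be the scan that confirms a response.

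If the cut falls in that gap, the participant stays in the denominator and leaves the numerator, because an unconfirmed PR is at best SD. Those exposed are participants who stop without progression. Some of them stop for treatment-related toxicity, which is the event the co-primary safety endpoint counts. At a small sample size one response moves ORR visibly, and dose selection is tied to this analysis.

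**Working it through.** The plan's sample size and target ORR are redacted, so there is no stated figure to reproduce. The check has four steps.

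**1. Can the cut precede a confirmation?** The week-6 scan window is 42 ± 7 = days 35-49 and the week-12 window is 84 ± 7 = days 77-91. The shortest scheduled gap is 77 − 49 = 28 days, so the week-12 scan can confirm a week-6 response. Suppose a first PR at week 6 and a toxicity stop on day 50. The trigger is met for this participant on day 50. The confirming scan falls 77 − 50 = 27 to 91 − 50 = 41 days later. If this participant is among the last to satisfy the trigger, the PR is unconfirmed at the cut.

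**2. Who is exposed?** With e = enrolment date, the trigger date is the latest, over all participants, of e + min(6 months, time to treatment stop). It waits for the last participant, so someone who stopped earlier keeps contributing scans in the meantime. Exposure needs three things together: late enrolment, a stop without progression, and a response still unconfirmed or not yet seen at the cut. A stop for progression already fixes best overall response (BOR).

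**3. Which direction?** The denominator is fixed and a confirmed response is normally permanent, so an earlier cut normally gives an equal or lower ORR. There is one exception. Appendix 6 (Sections 2.2.2 and 2.3.4) dates a confirmed equivocal new lesion or equivocal progression back to the initial scan, and BOR stops at first progression. Take a PR at week 6, then a PR at week 12 with an equivocal new lesion that is confirmed at week 18. Progression is then dated week 12 and the confirmation is lost. A cut between weeks 12 and 18 would overstate ORR.

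**4. How large?** One response is worth 100/N points: 5.0, 3.3, 2.5 or 1.7 at N = 20, 30, 40 or 60. Simulation compared confirmed responses at two cuts: the latest e + min(6 months, treatment stop), as written, and the latest e + min(6 months, progression), as amended. All inputs are assumptions, with true confirmed ORR 30% and N 20-60 in both sets, and confirmation 6 weeks after first response.

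- *Set A:* accrual 2-10 per month; median time to progression 3.5 months (about 15.2 weeks) in non-responders; first response at week 6/12/18/24 in 55/28/12/5%; toxicity stops 1%, 2% or 4% per week. The progression hazard is ln 2/15.2 = 4.56% per week, so the share of non-responders stopping before progression is 1/5.56 = 18%, 2/6.56 = 30% or 4/8.56 = 47%.
- *Set B:* accrual over 90-365 days; median time to progression about 110 days in non-responders; first response 60/25/10/5%; 10-30% non-progression stops by 6 months, equivalent to −ln(0.9)/26.1 = 0.4% to −ln(0.7)/26.1 = 1.4% per week.

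| Assumptions | Mean ORR difference (points) | Trials with at least one response affected |
|---|---|---|
| A, 1-2% per week | 0.02-0.26 | about 1-5% |
| A, 4% per week | up to about 0.7 | up to about 13% |
| B | 0.0-0.2 | 0.3-3.4% |

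**What the amended trigger leaves.** Six months is about day 183. A first response at week 18 is confirmed at week 24 (days 161-175), in time. A first response at week 24 needs the week-30 scan (days 203-217), which is too late. Under set A at N = 40 and 5 per month, the shortfall against full follow-up falls only from 0.29 to 0.25 points at 1% per week and from 0.34 to 0.26 at 2%. The largest gain in set B (N = 20, 365-day accrual, 30% stops) takes it from 29.93 − 29.56 = 0.37 to 29.93 − 29.74 = 0.19.

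**The case against.** The trigger says when the analysis will be performed and does not define a clinical data cutoff. The analysis details are deferred to a SAP to be finalized before database lock, and the redacted text of Section 10.1 may hold further timing rules. A final analysis is also planned, which could pick up late confirmations. The protocol now has one starting dose, so nothing shows that a shift of a few tenths of a point would alter a decision. All of this stands: it makes the point conditional and keeps it small. It does not reconcile the trigger with the estimand, and a later analysis does not protect a decision taken at the primary one.

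The rules on subsequent therapy add uncertainty about which off-treatment scans count. Section 10.3.2 and Appendix 6 Section 2.3.1 point to a cut-off at subsequent therapy, whereas Table 4-1 applies treatment policy. That affects only participants who start new therapy.

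Three stronger readings are tempting, and the documents do not support them:

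- *The early cut can only understate ORR.* The backdating rule in Appendix 6 gives a path to overstatement.
- *Any responder who stops for ILD is cut off that day.* The trigger waits for the last participant, so most such responders continue to be scanned before the cut.
- *The safety co-primary is compromised because the 30-day AE window is open.* That endpoint is treatment-related AEs leading to discontinuation, and the stop itself is known on the trigger day. The 30-day window belongs to the secondary safety estimand. It would also be open for participants still on treatment at month 6.

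**Conclusion.** The inconsistency is real and minor. The trigger accepts a treatment stop for any reason as the end of follow-up, while the primary efficacy estimand and the imaging rules do not. If the trigger date serves as the data cut, a confirmation can be missed in a late-enrolled participant who stopped without progression. The main effect is to understate ORR, with occasional movement the other way.

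The mean effect is roughly 0 to 0.3 points at toxicity stops of 1-2% per week and up to about 0.7 points at 4% per week. At least one response is affected in about 1-5% of simulated trials at the lower rates and up to about 13% at the highest. The documents give no stop rate for this dose and population, and the upper figures depend on the 4% assumption. The simulations do not model backdated progression. The sizes are illustrative, and the mismatch itself does not depend on them.

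**What to change.** In Section 5.1 and in the Protocol Summary, replace the alternative about stopping treatment with: *or have earlier documented progression, died, withdrawn consent for tumor assessment, or been lost to follow-up*. This ties the trigger to tumor-assessment follow-up, as the estimand does, and changes nothing in how participants are treated or scanned.

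The cost is one sentence in two places and a data cut about 0.2 to 4 weeks later on average in the simulated scenarios (set A).

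State alongside it that first responses at about week 24 remain unconfirmed at 6 months, because they need the week-30 scan. If the sponsor wants those covered, the trigger can also allow time for one confirmatory scan. In simulation that moves the cut about 6 to 9 weeks later than the current wording, so it is best treated as optional.
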